**Study Measurements:**

**Safety:**

- Ocular: visual acuity, intraocular pressure, biomicroscopy, ophthalmoscopy
- Systemic: vital signs, clinical laboratory (Chem-panel), hematology

Adverse event reporting

**Efficacy:**

**Primary Efficacy Endpoint:**

Comparison between drug-treated and vehicle-treated groups on changes of the severity grade of pterygium vascularity from baseline (Day 1) at Week 4;

**Secondary Efficacy Endpoints:**

Comparison between drug-treated and vehicle-treated groups on change from baseline (Day 1) at Weeks 2, 4, 8, 16 and 24 in:

- Corneal lesion length, defined from the anterior edge of the limbus onto the central cornea
- Corneal lesion area;
- Corneal lesion width;

Comparison between drug-treated and vehicle-treated groups on changes of the severity grade of pterygium vascularity from baseline (Day 1) at Weeks 2, 8, 16 and 24;

Changes from baseline (Day 1) at Weeks 2, 4, 8, 16, and 24 in:

- Corneal lesion length
- Corneal lesion area
- Corneal lesion width

Change in severity grade of pterygium vascularity from baseline (Day 1) at Weeks 2, 4, 8, 16, and 24

Comparison between drug-treated and vehicle-treated groups on change from baseline (Day 1) at Weeks 2, 4, 8, 16 and 24 in:

- Topographic astigmatism in diopters

Comparison between drug-treated and vehicle-treated groups on change from baseline (Day 1) at Weeks 2, 4, 8, 16 and 24 in:

Scores of Pterygium Symptom and Life Quality (PSLQ) questionnaire

**Statistical Methods:** Two database locks are planned for the study, interim and final. The interim analysis will be performed after at least 80% of patients have completed their week 4 visit or discontinued prematurely. The final analysis will be performed after study completion.

The O'Brien-Fleming group-sequential method will be used for a multiple-comparison adjustment of p-values for efficacy due to analyzing the data for both interim and final analyses. For the final analysis, a 2-sided test with p-value  $\leq 0.048$  will be considered statistically significant for all between and within treatment comparisons.

- In general, continuous data will be summarized with descriptive statistics (number of patients, mean, standard deviation, median, minimum and maximum) and will be analyzed using analysis of variance (ANOVA) techniques or 2-sample t-tests for between-group comparisons, and paired t-tests for within-group analyses. Categorical variables will be summarized by sample size (N), frequency count and percent, and analyzed using Pearson's chi-square test or Fisher's exact test. Ordinal variables will be analyzed using the Cochran-Mantel-Haenszel (CMH) or the Wilcoxon rank-sum test for between-treatment comparisons and the sign-rank test for within-treatment comparisons. No imputation for missing data will be performed.

**Duration of Study Follow-Up:** 1, 3, and 5 months after the completion of 28 days of continuous ocular dosing.

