## ATTACHMENT: SCHEDULE OF EVENTS

Study Procedures	Screening Days -60 to -7	Day 1 a	Week 2 (± 5 days)	Week 4 (± 5 days)	Week 8 (± 7 days)	Week 16 (± 7 days)	Week 24 (± 7 days)
Informed Consent/Authorization	X						
Inclusion/Exclusion Criteria	X	X					
Demographics	X						
Medical / Ocular History	X						
Pregnancy Test	X	X	X				
Serious Medical Events (SME)	X	X					
Subject ID Assignment	X						
Concomitant Medications/Concurrent Procedures	X	X	X	X	X	X	X
Pterygium Symptom and Life Quality (PSLQ) questionnaire	X	X	X	X	X	X	X
Vital Sign measurements (blood pressure, heart rate, body temperature)	X	X	X	X	X	X	X
Hematology & Blood Chemistry	X			X			X
Pterygium Photography b		X	X	X	X	X	X
Pterygium Vascularity Assessment	X	X					
Pterygium Morphology Assessment	X	X					
Pterygium Size Assessment	X	X					
Biomicroscopy	X	X	X	X	X	X	X
Topographic Astigmatism	X	X	X	X	X	X	X
Best-Corrected Visual Acuity	X	X	X	X	X	X	X
Intraocular Pressure	X	X	X	X	X	X	X
Ophthalmoscopy (dilated)	X	X		X			X
Adverse Events		X	X	X	X	X	X
Randomization		X					
Study Medication		Dispense	Collect	Collect	Collect		
Exit							X

a All measurements at baseline Day 1 are prior to the instillation of first dose

b Efficacy endpoints will be assessed using pterygium photography at an independent image reading center

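### PSLQ and topographic astigmatism have two pre-dose readings but are compared on unadjusted change from Day 1; adding both readings as covariates is cheap, with most of any gain likely to come from Day 1

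*Combined protocol and SAP*

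**What the plan says.** Under Secondary Efficacy Endpoints, "Topographic astigmatism in diopters" and "Scores of Pterygium Symptom and Life Quality (PSLQ) questionnaire" are each introduced by the same wording: "Comparison between drug-treated and vehicle-treated groups on change from baseline (Day 1) at Weeks 2, 4, 8, 16 and 24 in". The Statistical Methods paragraph that follows says continuous data will be "analyzed using analysis of variance (ANOVA) techniques or 2-sample t-tests for between-group comparisons". It names no covariate, and it assigns ordinal variables to CMH or Wilcoxon tests.

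In the Schedule of Events, the rows "Pterygium Symptom and Life Quality (PSLQ) questionnaire" and "Topographic Astigmatism" are marked in the column "Screening Days -60 to -7", on Day 1, and at every later visit. Footnote a adds: "All measurements at baseline Day 1 are prior to the instillation of first dose". Each patient therefore has two pre-dose values of both measures. No use of the Screening value is described, and neither measure is a listed entry criterion.

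**The concern.** A questionnaire score and a topography reading both vary from visit to visit. When the outcome is change from one baseline reading, all the noise in that reading passes into the change. Covariate adjustment removes part of it, and a second pre-dose reading may remove more. Both readings precede treatment, so prespecified adjustment for them does not bias the comparison.

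The point is specific to these two endpoints. Lesion size and vascularity are read from photographs, which start on Day 1, so those endpoints have no like-for-like second baseline. What is at stake is precision on two secondary endpoints in a 50-patient trial.

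**Working it through.** **Inputs.** Total N = 50 (synopsis, Number of Subjects). The plan states no SD, correlation, effect size or power for either endpoint, so it offers no figure to reproduce. All correlations below are assumptions.

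**Notation.** Variance is 1 at each visit. r = correlation of Day 1 with follow-up; s = correlation of Screening with follow-up; q = correlation of Screening with Day 1.

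**Formulas.**
- Planned change from Day 1: 2(1 − r).
- ANCOVA on Day 1: (1 − r²) × (1 + 1/46).
- ANCOVA on Day 1 and Screening: [1 − (r² + s² − 2rsq)/(1 − q²)] × (1 + 2/45). With all correlations equal to r, the bracket is 1 − 2r²/(1 + r).

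The factors 1/46 and 2/45 are the cost of estimating one or two covariates with N = 50. With Day 1 as a covariate, ANCOVA of change and ANCOVA of the follow-up value give the same treatment estimate, so the variances are comparable.

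**Step 1: equal correlations.**

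| r | Change | Day 1 ANCOVA | Two covariates | Day 1 / change | Two / change | Two / Day 1 |
|---|---|---|---|---|---|---|
| 0.5 | 1.000 | 0.766 | 0.696 | 0.77 | 0.70 | 0.91 |
| 0.7 | 0.600 | 0.521 | 0.442 | 0.87 | 0.74 | 0.85 |
| 0.9 | 0.200 | 0.194 | 0.154 | 0.97 | 0.77 | 0.79 |

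The Day 1 covariate supplies about 23 of the 30 percentage points at 0.5, 13 of 26 at 0.7, and 3 of 23 at 0.9. Only the last column measures what Screening adds: 9% to 21%, when it predicts follow-up as well as Day 1 does.

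**Step 2: Screening less predictive than Day 1.**

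| r | s | q | Two / Day 1 |
|---|---|---|---|
| 0.8 | 0.75 | 0.8 | 0.927 |
| 0.7 | 0.60 | 0.7 | 0.975 |
| 0.8 | 0.70 | 0.8 | 0.994 |
| 0.7 | 0.49 | 0.7 | 1.022 |

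The range is a 7% gain to a 2% loss in variance, or about 4% better to 1% worse in standard error (√0.927 = 0.963; √1.022 = 1.011). The last row is geometric decay (0.49 = 0.7 × 0.7). Screening then adds nothing, and the loss is purely (1 + 2/45)/(1 + 1/46) = 1.022.

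**Step 3: against the plan when Screening adds nothing.** The ratio is (1 + r)/2 × 1.0444: 0.78 at r = 0.5, 0.89 at 0.7 (0.51 × 1.0444/0.60), and 0.99 at 0.9. It reaches 1 where 1 + r = 2/1.0444, so r is about 0.915. Above that there is a small loss, at most 4.4%.

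**Step 4: why not average the two readings.** Change from the two-reading mean has variance 1 + (1 + q)/2 − r − s. With equal correlations this is 1.5(1 − r), which is 0.75 of the planned variance. With (0.7, 0.49, 0.7) it is 0.66, and 0.66/0.60 = 1.10, worse than Day 1 alone. Two separate covariates let the data set the weight of the older reading.

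**The case against.** The strongest reply is that nothing is broken. Change from a pre-dose Day 1 value is a valid, unbiased comparison, and a second covariate on two secondary endpoints is an efficiency preference. That stands, and it limits the weight of the point without removing it.

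The documents also give reasons to doubt the Screening value. It may be taken up to 60 days before Day 1. Major Exclusion Criteria times the washouts to Day 1: 3 days for soft lenses, 3 weeks for rigid or hard lenses, and 2 weeks for topical medication in the study eye. Some Screening topography or symptom scores may therefore be taken while lenses or drops are still in use. This also stands, and is why Step 2 is a better guide than the last column of Step 1.

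A reader might infer three stronger claims:
- That the second reading is worth 23% to 30% of the variance. Those are the gains of both covariates over the plan, and much of them belongs to Day 1 when correlation is moderate.
- That 80% power would become about 90%. That figure is for averaging the two readings under equal correlations, with 25 per arm and two-sided alpha 0.048. The allocation ratio is not stated, and averaging can lose precision.
- That the plan has deliberately discarded the Screening value. The document is labelled a short protocol, describes its methods in general terms, and uses a phrase (ANOVA techniques) that does not strictly exclude a covariate. It supports only the statement that none is named.

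Finally, the PSLQ scale is not described. If the scores are treated as ordinal, the plan assigns CMH or Wilcoxon tests, and these calculations do not carry over directly.

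**Conclusion.** The point holds as a cheap improvement on two secondary endpoints. It is not an error or a bias in the plan, and the documents do not support reading it as one.

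Against the planned change score, the Day 1 covariate is worth about 23% of the variance at correlation 0.5, 13% at 0.7 and 3% at 0.9. Beyond that, Screening realistically adds about 0% to 7%, with a worst-case loss of about 2% against Day 1 adjustment. The further 9% to 21% requires Screening to predict follow-up as well as Day 1, which the time gap and the washout timing make doubtful. At high correlation the Day 1 covariate does little, so almost all of any gain there depends on Screening.

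These sizes rest on assumed correlations, equal variances across visits, N = 50 with complete data, and PSLQ analysed as a continuous score.

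**What to change.** Before unmasking, add one sentence to the SAP: at each post-baseline visit, topographic astigmatism and PSLQ score will be compared by ANCOVA of change from Day 1, with treatment as the factor and the Day 1 and Screening values as two separate covariates, not averaged. The plan has no repeated-measures model, so a visit-by-visit analysis fits it as written. State that the PSLQ score is analysed as continuous; if it is to be ordinal, leave it out of this change.

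The cost is SAP wording and one degree of freedom for the Screening covariate, with no new assessment. Because the plan rules out imputation, also say how a patient without a Screening value is handled; otherwise that patient drops out of the model. If the sponsor prefers one covariate, Day 1 alone secures the more dependable part of the gain.

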Methodology: Strategy: 
 
Evaluate ocular and systemic safety profile of CBT-001 ophthalmic solution in patients with primary or recurrent pterygium, that are associated with moderate to severe pterygium vascularity;
 
Establish whether CBT-001 is efficacious in reducing pterygium vascularity;
 
Assess whether CBT-001 is efficacious in inhibiting pterygium lesion growth;
 
 Plan: A multicenter, double-masked, vehicle-controlled and parallel study is designed with 28 days TID repeat ocular dosing of vehicle and the highest tolerable dose (e.g., 0.2%), followed by 5-month post dose observation. Ophthalmic and physical examinations will be performed at screening, Day 1 and weeks 2, 4, 8, 16, and 24. External photograph of the pterygium eye will be taken using a digital camera and the lesion length, width and area as well as pterygium vascularity will be measured or graded from these images at an independent image reading center.	
Number of Subjects: 50 patients with primary or recurrent pterygium.	
Diagnosis and Main Criteria for Eligibility: Major Inclusion Criteria 
 
Primary pterygium with 0.6-3.5 mm lesion length from the anterior edge of limbus to the central cornea, associated with pterygium vascularity <math>\geq</math> Grade 3 using the 5-point Pterygium Hyperemia Grading Scale
 
	

- a. A minimum of Grade 3 (moderate) pterygium vascularity in the study eye at the screening (day -60 to day -7) and baseline (day 1) visits, using the 5-point Pterygium Hyperemia Grading Scale (0 = absent, 1 = trace, 2 = mild, 3 = moderate, 4 = severe);
- b. About 0.6-3.5 mm of encroachment of the pterygium onto the cornea of the study eye at the screening (day -60 to day -7) and baseline (day 1) visits as measured by slit lamp examination (investigator assessment). The measurement is as described by Welch et al [Welch et al, 2011]. A standard magnification of 16 is used and the variable aperture is focused on the pterygium from the limbus to the apex. Reading the size on the slit lamp scale, measurements are taken from the limbus to the apex of the lesion on the cornea and recorded to the nearest tenth of a millimeter.

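### The 0.048 significance label also covers within-arm change from baseline, so a change shared with vehicle can be reported as a statistically significant efficacy endpoint

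*Combined protocol and SAP*

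**What the plan says.** All references are to the synopsis and the attached schedule in the combined protocol and SAP.

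- **Statistical Methods.** The O'Brien-Fleming method is used for a "multiple-comparison adjustment of p-values for efficacy due to analyzing the data for both interim and final analyses". A two-sided p of 0.048 or less at the final analysis "will be considered statistically significant for all between and within treatment comparisons". Paired t-tests are named for within-group analysis of continuous data and "the sign-rank test for within-treatment comparisons" for ordinal data.
- **Primary Efficacy Endpoint.** One between-arm item: "Comparison between drug-treated and vehicle-treated groups on changes of the severity grade of pterygium vascularity from baseline (Day 1) at Week 4".
- **Secondary Efficacy Endpoints.** Lesion length, area, width and vascularity each appear twice: once as a comparison of drug with vehicle, and once as plain change from baseline. An example of the second kind is "Change in severity grade of pterygium vascularity from baseline (Day 1) at Weeks 2, 4, 8, 16, and 24". Astigmatism and the PSLQ questionnaire appear only as comparisons.
- **Eligibility.** Entry needs "A minimum of Grade 3 (moderate) pterygium vascularity in the study eye at the screening" and again at Day 1, on a scale from 0 to 4. Day 1 is the baseline.
- **Schedule of Events, footnote b.** "Efficacy endpoints will be assessed using pterygium photography at an independent image reading center".

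No sentence in the supplied short protocol ranks the two kinds of secondary result or calls either of them descriptive.

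**The concern.** A within-arm test asks whether patients changed after Day 1. It does not ask whether the drug caused the change, which is what the vehicle arm is there to answer. The plan lists these changes as efficacy endpoints and gives them the same threshold and label as a drug-versus-vehicle difference.

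The overlap with the primary endpoint makes this matter most. Vascularity at Week 4 is both the primary between-arm comparison and one of the within-arm endpoints. If the primary comparison failed, the drug arm's own Week 4 fall could still be reported, under the stated rule, as a statistically significant efficacy result.

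A fall shared by both arms is plausible for vascularity. Patients enter only if graded 3 or higher on a scale that stops at 4, and the last qualifying visit is the baseline. Some regression toward lower grades could follow in either arm.

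The same labelling applies to the aim "Assess whether CBT-001 is efficacious in inhibiting pterygium lesion growth". Only secondary tests address it: 15 between arms and 15 within each arm.

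**Working it through.** **1. The plan's own threshold.** A classical two-look O'Brien-Fleming boundary, with overall two-sided alpha of 0.05 (assumed) and the interim at half the information, gives a final level of 0.04799, which rounds to 0.048. The figure therefore allows for two looks at one hypothesis. It makes no allowance for number of endpoints, number of visits or type of comparison.

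**2. Count of tests, from the Secondary Efficacy Endpoints list.**

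- Within-arm: 4 measures × 5 visits = 20 per arm.
- Between-arm: lesion length, area and width 3 × 5 = 15; vascularity 4; astigmatism 5; PSLQ 5 (taken as one score). Total 15 + 4 + 5 + 5 = 29.

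**3. One data set, both of the plan's tests.** Assume 25 per arm; the total of 50 is stated but the allocation ratio is not. Let 6 patients in each arm fall one grade and 19 stay the same.

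- Drug arm, exact signed-rank test, zeros dropped: all six non-zero changes go the same way, so p = 2 × 0.5^6 = 0.03125. This is below 0.048. Five falls would give 2 × 0.5^5 = 0.0625, so six is the smallest number that earns the label when nobody rises.
- Drug versus vehicle, rank-sum test with tie correction and no continuity correction. With only two outcome values, z = (difference in proportions) / √[p(1 − p) × N/(N − 1) × 2/n], where p is the pooled proportion falling, N = 50 and n = 25. The difference is 0, so p-value = 1.0.
- With 6 falls on drug and 3 on vehicle: difference 0.12, pooled proportion 9/50 = 0.18, z = 0.12 / √(0.18 × 0.82 × 50/49 × 0.08) = 0.12 / 0.110 = 1.09, p-value = 0.27.

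**4. How often this pattern could arise.** Give both arms the same true probability of a one-grade fall and no rises. Sum the two binomial distributions exactly over all outcomes where the drug arm has six or more falls (signed-rank p ≤ 0.048) and the rank-sum p exceeds 0.048.

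| True fall rate in both arms | 25 per arm | 20 per arm |
|---|---|---|
| 10% | 2% | 1% |
| 15% | 14% | 5% |
| 20% | 36% | 18% |
| 30% | 78% | 56% |

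The between-arm test rejects in 4% to 5% of trials in every row. The table shows the power of the within-arm test to detect a real change that has nothing to do with drug. These are not type I error rates.

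**5. Side calculation.** If all 29 between-arm null hypotheses are true, the expected number of false positives is 29 × 0.048 = 1.39, whatever the correlations among them.

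**The case against.** **The tests are valid.** A within-arm p-value correctly answers whether mean change differs from zero, and the plan nowhere says that it demonstrates efficacy. Items meant as contrasts with vehicle say so, and the design and primary endpoint point to drug versus vehicle. All of this stands. It does not remove the problem, because the changes are listed as efficacy endpoints and the written rule expressly gives them the label.

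**The mechanism is limited.** Grade 3 or higher is required at two visits at least a week apart, which weakens regression to the mean, and reading-center grading from photographs may weaken it further. This stands in part: the effect may be small but is not excluded. It covers vascularity only, which is 5 of the 20 within-arm tests per arm. A reader might infer that lesion size would also shift in both arms. The documents give no reason for that, since lesion length at entry is bounded on both sides (about 0.6 to 3.5 mm).

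**Uncontrolled secondary tests are ordinary in a 50-patient Phase 2a study.** This stands. A reader might infer that the 29 between-arm tests require a multiplicity correction. How to label them is a trade-off, and leaving them uncorrected is not an error in the plan.

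**The source is a short protocol.** A fuller analysis plan might contain the missing sentence. The point is therefore confined to the supplied text, which states a rule covering within-arm tests and does not merely leave detail out.

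**Conclusion.** The concern holds as a labelling fault. Following the stated rule, a change seen equally in drug and vehicle can be called a statistically significant efficacy endpoint, including at the primary measure and visit. The worked example (0.031 within the drug arm, 1.0 against vehicle) shows this with the plan's own tests.

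The likely frequency is unknown. It runs from about 1% to 78% across assumed shared fall rates of 10% to 30% with 20 or 25 patients per arm. The fall rates, the absence of rises and the equal allocation are assumptions; no figure in the documents supports a particular value.

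A reader might also infer that the primary result is compromised. The secondary and within-arm tests do not inflate the single Week 4 drug-versus-vehicle comparison. Whether 0.048 suits an interim at 80% or more of patients through Week 4, when it matches a boundary with the interim at half the information, is a separate question not settled here. The plan should be corrected, but the problem is minor to moderate.

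**What to change.** In Statistical Methods, remove within-treatment comparisons from the 0.048 rule. Present within-arm changes descriptively with confidence intervals, with any p-value marked as nominal, and add a sentence that efficacy conclusions rest on drug versus vehicle. In the Secondary Efficacy Endpoints list, mark the items without a vehicle comparison as descriptive.

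Optionally, mark the 29 secondary between-arm p-values as nominal. If a formal statement on lesion growth is wanted, name one lesion measure and one visit in advance.

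The cost is a few sentences. Data collection and sample size do not change; fewer results can be called significant.

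### Adding the Day 1 value as a covariate (ANCOVA) to the continuous change-from-Day-1 comparisons is a cheap precision gain; the planned tests are valid without it

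*Combined protocol and SAP*

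**What the plan says.** The methods text is one general paragraph in the synopsis (Statistical Methods).

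- Continuous data: "will be analyzed using analysis of variance (ANOVA) techniques or 2-sample t-tests for between-group comparisons".
- Ordinal data: "Ordinal variables will be analyzed using the Cochran-Mantel-Haenszel (CMH) or the Wilcoxon rank-sum test for between-treatment comparisons".
- Primary endpoint: drug against vehicle on "changes of the severity grade of pterygium vascularity from baseline (Day 1) at Week 4". The secondary between-arm comparisons are also of changes from Day 1: lesion length, area and width, topographic astigmatism, the PSLQ score, and the vascularity grade at other visits.
- Day 1 data: "All measurements at baseline Day 1 are prior to the instillation of first dose" (Schedule of Events, footnote a). Photography, astigmatism and PSLQ are all scheduled on Day 1. Size and vascularity come from one source: "lesion length, width and area as well as pterygium vascularity will be measured or graded from these images at an independent image reading center".
- Size and timing: "50 patients with primary or recurrent pterygium"; "The interim analysis will be performed after at least 80% of patients have completed their week 4 visit or discontinued prematurely".

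No Day 1 covariate, stratum or stratification factor is named anywhere. The documents do not say whether the grade change or the PSLQ score is treated as ordinal or continuous. They give no allocation ratio, SD, correlation or power.

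**The concern.** A change score fixes the slope of the follow-up value on the Day 1 value at 1. If the true slope is different, the change keeps some variance that the Day 1 value could explain. ANCOVA estimates the slope and removes that variance. In a trial of 50 patients, with about 40 at the interim, precision is scarce, and the covariate needs no new data.

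A smaller matter concerns the primary endpoint. If the grade change is ordinal, the plan offers two tests joined by an *or*, with no rule for choosing between them at the interim or the final analysis.

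**Working it through.** **Inputs.** From the documents: N = 50; the interim at 80% or more, so about 0.8 x 50 = 40 patients; two-sided 0.048 at the final analysis. Assumed, because the documents do not give them: rho, the correlation between the Day 1 and follow-up values; k = Day 1 SD / follow-up SD; the allocation; and the slopes within each arm. No stated power or effect size accompanies the 50, so there is no planning figure to reproduce.

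**Step 1: common slope in both arms.** In units of the follow-up variance, the change has variance 1 + k^2 - 2 rho k = (1 - rho^2) + (k - rho)^2. ANCOVA has residual variance 1 - rho^2. Estimating the slope multiplies the variance of the treatment difference by (N - 3)/(N - 4). Hence

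ratio (ANCOVA / change score) = (1 - rho^2)/(1 + k^2 - 2 rho k) x (N - 3)/(N - 4).

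At N = 50 the last factor is 47/46 = 1.022. For example, rho = 0.5 and k = 1 give 0.75/1.00 x 1.022 = 0.766.

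| rho | k = 1.0 | k = 0.8 | k = 0.7 |
|---|---|---|---|
| 0.5 | 0.77 | 0.91 | 0.97 |
| 0.7 | 0.87 | 1.00 | 1.02 |
| 0.9 | 0.97 | 0.97 | 0.84 |

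Simulation (40,000 runs) agrees: 0.767, 0.867 and 0.973 for the k = 1 column.

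**Step 2: what this means for power.** Take an effect for which the change-score test has 80% power at 0.048. With k = 1, ANCOVA has about 89%, 85% and 81% at rho 0.5, 0.7 and 0.9.

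**Step 3: the downside with a common slope.** The first factor never exceeds 1 and equals 1 only when k = rho. The most that ANCOVA can lose is therefore 47/46, or 2.2% more variance, which takes 80% power to about 79%. At N = 40 the factor is 37/36 = 1.028, a 2.8% loss; with k = 1 the ratio there is 0.77 at rho 0.5 and 0.98 at rho 0.9. ANCOVA loses only when |k - rho| < sqrt((1 - rho^2)/(N - 4)). At N = 50 and rho 0.7 that means a follow-up SD 1.24 to 1.68 times the Day 1 SD.

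**Step 4: different slopes in the two arms.** Let the slopes be b1 (drug) and b0 (vehicle), with the Day 1 SD set to 1 and residual SD s. ANCOVA uses approximately the pooled slope b = (n1 b1 + n0 b0)/(n1 + n0). To a large-sample approximation:

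- ANCOVA variance: (b1 - b)^2/n1 + (b0 - b)^2/n0 + s^2(1/n1 + 1/n0)
- Change-score variance: (b1 - 1)^2/n1 + (b0 - 1)^2/n0 + s^2(1/n1 + 1/n0)

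With 1:1 allocation, b is the midpoint of the two slopes, which minimises the first expression. ANCOVA then cannot exceed the change score except by the small slope penalty. With unequal allocation this protection goes. For 33:17, b1 = 0.4, b0 = 1.1 and s = 0.4:

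- b = (33 x 0.4 + 17 x 1.1)/50 = 0.638
- ANCOVA: 0.0143 + 0.0143 = 0.0285
- Change score: 0.0115 + 0.0143 = 0.0258
- Ratio: 1.108, or 1.13 after the 1.022 factor

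Simulation at 33:17, with s = 0.4 or 0.7 and slope pairs 0.4/1.1, 0.5/1.1 and 0.6/1.2, gives losses of about 7-19%. At 25:25 the same slopes give ratios of about 0.84 to 1.01.

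**Step 5: the primary endpoint, if ordinal.** This simulation is illustrative: slope, grade mix, effect, error SD and allocation are all assumed. It compares Wilcoxon with the van Elteren test stratified by Day 1 grade, at 25:25, with 30% of eyes at Grade 4.

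| Week 4 on Day 1 slope | Wilcoxon power | van Elteren power |
|---|---|---|
| 0 | 0.611 | 0.716 |
| 0.5 | 0.703 | 0.725 |
| 1 | 0.721 | 0.712 |

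Over other effects, SDs, grade mixes and a 2:1 allocation, the difference runs from -1.8 to +24.6 points. Each test alone holds its level (null rejection 4.5-5.0%). Reporting the better of Wilcoxon and an unstratified integer-score CMH, the two tests as written, gives 5.0-5.6% against 4.8% nominal.

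**The case against.** The strongest reply is that this is a preference. The planned tests are valid under randomization. The methods paragraph is expressly general, in a short-form protocol, and its wording leaves room for adjustment: ANOVA techniques can include a covariate and CMH can include strata. All of that stands. A reader might infer that the plan is wrong or that it bars adjustment; the documents support neither. What remains is that an adjustment merely permitted is not one specified, so its precision is not assured.

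Second, a severity grade falls most naturally under the ordinal sentence, so ANCOVA may reach only secondary endpoints. This stands, and it limits the importance of the point.

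Third, the gain rests on unknown inputs. If lesion length tracks closely over four weeks (rho 0.9 or more, with k near 1), the gain is 3% or less. A reader might also take 2.2% as the worst possible loss in all cases. Step 4 shows that it needs a common slope or 1:1 allocation, and the documents state neither.

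Fourth, a reader might infer that the stratified test is the better primary analysis. The range in Step 5 includes losses, and nothing in the documents says which slope applies. Nor should the risk from the open choice of test be overstated. A type I error of up to 7.8% arises only if a stratified test is one of the options, and the plan names no stratum.

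**Conclusion.** The point holds as a low-cost improvement that the sponsor could adopt. On the continuous endpoints, the variance reduction is about 23%, 13% and 3% at rho 0.5, 0.7 and 0.9, given N = 50, equal SDs at both times and a common slope. The loss is bounded at about 2.2% (2.8% at 40 patients) under a common slope, and at about the same under 1:1 allocation. Under 2:1 allocation with strongly different slopes, losses of about 7-19% are possible.

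Confidence is high for the formula and moderate overall, because rho, k, the slopes and the allocation are assumed. For an ordinal primary endpoint, the documents support naming one test in advance, but they do not support preferring the stratified one.

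**What to change.** Before the interim database lock:

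1. For endpoints analysed as continuous (lesion length, area and width, topographic astigmatism, and PSLQ if so treated), replace the 2-sample t-test with ANCOVA of the change from Day 1, with treatment and the Day 1 value as terms. Report the adjusted difference with its confidence interval. The outcome is still the change, so the stated endpoints do not move. State the allocation ratio, because the bound on the loss depends on it.
2. State whether the primary grade change is ordinal or continuous. If continuous, use the same ANCOVA. If ordinal, name one test for both the interim and the final analysis. Unstratified Wilcoxon is acceptable. So is a van Elteren test stratified by the reading-center Day 1 grade (for example 4 against 3 or lower), since the reading center is the source of the endpoint: "Efficacy endpoints will be assessed using pterygium photography at an independent image reading center".

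Cost: one degree of freedom, and no new data, visits or patients. Because the only methods text supplied is in the protocol synopsis, the change may need a protocol amendment as well as SAP wording.
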